Study Protocol and Statistical Analysis Plan

Investigating Hearing Aid Frequency Response Curves – ID#3167

July 24, 2024

NCT05521308

Investigating Hearing Aid Frequency Response Curves – ID#3167

1 Objectives and hypotheses of the clinical investigation

1.1 Purpose of the clinical investigation claims for clinical performance, effectiveness or safety of the investigational device that are to be verified

The study is an exploratory study in which we are evaluating various frequency gain curves for streaming and acoustic programs. Participants will be asked to rate overall preference while streaming and overall program preference in the presence of live stimuli. This clinical investigation is being conducted to determine if it is beneficial to implement new frequency gain curves for our products.

1.2 Primary and Secondary Objectives

Primary Objective

Determine if applying frequency specific gain changes to our current streaming programs are preferred by hearing aid users when compared to our current streaming program.

Secondary Objectives

- Determine if applying frequency specific gain changes to our current acoustic programs are preferred by hearing aid users when compared to our current acoustic programs.
- Determine if a proposed frequency response curves will impact speech intelligibility when compared to our current frequency response curves.

2 Design of the clinical investigation

2.1 General

2.1.1 Design Type

This clinical investigation is an interventional study and conducted at one investigation site. The investigation consists of a single group of participants that will be tested in all conditions (cross-over). When doing the streaming task, both the participant and the investigator will be blinded to the gain curves that are being compared as the software will randomize this. During the live preference ratings, participant's will be blinded to the program they are under, however the investigator will know the program as they will program the hearing aids prior to testing.

There are three gain curves that will be tested for the streaming task (Variations #1, #2, and #3) and two gain curves (Standard curve and Variation #4) that will be tested for live ratings task. Please note that changing between frequency curves is done simply by clicking a button on the hearing aid or via a mobile app. This will be done for the US matrix test and the live sound quality ratings task. For the streaming sound quality task, participants will compare pre-recorded stimuli, which have the various gain curves applied, via hearing aids. Frequency curves (i.e., interventions) can be toggled back and forth via the ratings software. Therefore, multiple gain curves (i.e. interventions) are compared simultaneously in each task (outcome measure) and participants can go back and forth between interventions during a task. This is done to allow participants to make accurate preference selections when comparing the various curves. The US matrix test is the only task in which switching back and forth during a measurement is not allowed

as it is an objective measure of speech recognition and SRT50 scores are recorded per condition tested (unaided, standard curve, and variation #4). Switching will only occur between measurements for the US Matrix test task.

Streaming Program Interventions
Variation #1
Variation #2
Variation #3
Acoustic Program and US Matrix Test Interventions
Standard Curve
Variation #4

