3.3.2 Primary Endpoint Analysis

The primary analysis will be the subjective ratings participants provide for the streaming task. Subjective ratings will be tallied to see which frequency response curve was preferred the most. Participants will be presented with two samples at a time and will choose which sample they prefer. For example, if Sample A was preferred over Sample B, then Sample A gets a score of 1. If Sample B was preferred over Sample A, then Sample B gets a score of 1. In some trials, if the participant does not notice a difference between the two samples, then neither sample will get a score. At the end of the task, scores will be tallied to determine which sample was preferred the most overall. There will be 3 different samples. The minimum value for the tallied score would be 0 (the sample was not preferred at all) and the maximum value would be 2 (implying that the sample was preferred in all trials in which it was involved). Higher scores mean that the sample was preferred more and lower scores mean the sample was not preferred as much when compared to the other samples.

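### The primary objective compares new streaming curves with the current streaming program, but none of the three streaming curves is identified as that program and the primary tally isolates no comparison with it

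*Combined protocol and SAP*

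**What the plan says.** The primary objective in section 1.2 is comparative: it asks whether streaming programs with frequency-specific gain changes are "preferred by hearing aid users when compared to our current streaming program".

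Section 2.1.1 describes what is tested: "There are three gain curves that will be tested for the streaming task (Variations #1, #2, and #3". The intervention list in the same section repeats those three labels and adds nothing. For the other arm of the study the reference is explicit: "two gain curves (Standard curve and Variation #4) that will be tested for live ratings task". On masking of the streaming task, the section says "both the participant and the investigator will be blinded to the gain curves that are being compared as the software will randomize this".

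The primary analysis in section 3.3.2 works on pairs. The preferred sample of each pair scores 1. For ties, "if the participant does not notice a difference between the two samples, then neither sample will get a score". It states "There will be 3 different samples" and that "the maximum value would be 2 (implying that the sample was preferred in all trials in which it was involved". The rule for reading the result is "scores will be tallied to determine which sample was preferred the most overall". No sample is named as the reference, and no pair is singled out.

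**The concern.** The primary question needs a known reference curve, and a result that sets each new curve against it. The plan clearly supplies neither. A reader cannot tell from the text whether the current program is in the streaming task at all. Even if it is, the result the plan will report is a ranking of three samples and not a comparison with the current one.

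The consequence is practical. Section 1.1 says the study is to help decide whether new gain curves are worth implementing. A curve reported as the overall favourite could be taken as an improvement on the existing product in either of two situations where that does not follow: the existing product was never in the comparison, or it was and more participants preferred it to the winner.

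**Working it through.** **Inputs.** Three streaming samples, scores from 0 to 2, 1 point to the preferred sample of a pair, none to either if no difference is noticed (section 3.3.2); 25 participants (section 3.1). Assumption: one judgment per pair per participant, which the documents do not state but which fits the maximum score of 2.

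**Step 1: is there room for an unlisted reference?** With k samples there are k(k−1)/2 pairs and each sample is in k−1 of them.
- k = 3: 3 pairs, each sample in 2, so the maximum score is 2. This reproduces the plan's figure.
- k = 4: 6 pairs, each sample in 3, so the maximum score would be 3. This does not match.

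So either one of Variations #1 to #3 is the current program, or the current program is not in the streaming task.

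**Step 2: which pairs answer the primary question?** There are 25 × 3 = 75 judgments in all.
- No Variation is the current program: 0 of 3 pairs, 0 of 75 judgments.
- One Variation is: 2 of 3 pairs, 25 × 2 = 50 of 75 judgments. The other 25 compare the two new curves with each other, and they enter the tally with equal weight.

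**Step 3: can the tally point the wrong way when the current program is included?** Call the current program C and the new curves A and B. A first-ranked curve earns 2 points, a second-ranked 1, a third-ranked 0.

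| Participants | Ranking | A | C | B |
|---|---|---|---|---|
| 13 | C > A > B | 13 | 26 | 0 |
| 10 | A > C > B | 20 | 10 | 0 |
| 2 | A > B > C | 4 | 0 | 2 |
| 25 | Total | 37 | 36 | 2 |

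The total is 37 + 36 + 2 = 75, as it should be. Head to head:
- C against A: 13 to 12, so 13/25 = 52% prefer the current program.
- C against B: 23 to 2.
- A against B: 25 to 0.

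The current program beats both new curves, yet A has the highest tally because it collects all 25 points against B and C collects only 23.

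**Step 4: what drives the result?** Move the last two participants to A > C > B. The count of C against A stays at 13 to 12. The tallies become A = 13 + 24 = 37, C = 26 + 12 = 38, B = 0, and the current program is first. The winner changes although nobody changed their view of A against C; only the placing of B moved. That is the sense in which the tally does not isolate the primary comparison.

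**Step 5: how often?** The documents give no preference rates, so any frequency is an assumption. In simulated studies of 25, a new curve is strictly first while a majority prefer the current program to it in about 4% of studies if all six strict rankings are equally likely. The figure is about 9% if each of the three judgments is an independent even choice. Neither model allows no-difference answers.

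**The case against.** **One Variation may be the current program under a neutral number.** This is plausible and would suit a task in which participant and investigator are both blinded. For that reason a reader should not infer that the current program is absent from the streaming task; the text does not show that. What stands is that the plan does not say which it is. Blinding during the task does not prevent the plan from fixing the mapping in advance.

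**Summed wins are a usual summary of paired comparisons, and the study is exploratory.** Both are true. If one Variation is the current program, its tally can be set beside the others, and the judgments needed for a direct comparison are collected anyway. On that reading the flaw is in the rule and not in the data. But the exploratory label excuses the lack of a formal test, not an unidentified comparator, because the stated objective is itself a comparison.

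**The reversal example is selected and the judgment count is assumed.** This is also fair. Visit 2 is planned for about two hours with streamed ratings as its only test, so there may be several sound samples and more than three judgments per participant. The numbers above would then describe one set of three pairs. That tallies mix relevant and irrelevant pairs does not depend on the count.

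**Conclusion.** The point holds. As written, the streaming task either cannot answer the primary objective or answers it with a rule that can name a winner which loses head to head to the current program. Which of these applies cannot be settled from the documents. The size is 0 of 3 relevant pairs in the first case. In the second it is 2 of 3, mixed with a third, with a concrete reversal at 37, 36 and 2. The counts assume 25 participants and one judgment per pair.

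Three stronger readings are not supported:
- **That a reversal is likely.** It is possible rather than expected, and the two rates above differ because their assumptions differ.
- **That the opposing majority has a fixed upper limit.** Any such limit depends on each participant's three answers fitting a single ranking, which the plan does not require.
- **That the 90% power in section 3.1 is too low for the two comparisons.** The plan proposes no test for them and gives no effect size, so this cannot be judged here.

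**What to change.** Reconcile sections 1.2, 2.1.1 and 3.3.2 in one of two ways.

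(a) **If one Variation is the current program:** say which one in sections 2.1.1 and 3.3.2. Make the two pairs that contain it the primary comparisons. For each pair, report three counts: participants preferring the Variation, preferring the current program, and noticing no difference. Keep the overall tally as a descriptive summary.

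(b) **If none is:** restate the primary objective as a ranking of three candidate curves, and make no claim about preference over the current program.

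Option (a) costs wording plus two pairwise counts from judgments the task already collects. Option (b) costs wording only. Neither needs more participants, visits or listening time.

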2.2 Procedures

2.2.1 Investigation-related Procedure

Recruitment paths:

- Our internal database will be used to see if any potential participants who fit the inclusion criteria are available.
- Referrals from Hearing Healthcare Providers in the Kitchener and surrounding areas will be requested. HCPs will be contacted and provided with the recruitment materials.

Tasks

During the first appointment, participants will complete the speech in noise test and complete the live preference ratings task. During the second appointment, participants will complete the streaming preference ratings task.

Visit 1 Approximately 2 Hours	
• Study consent form and related forms will be reviewed and signed.• Hearing test will be completed (including otoscopy, tympanometry, speech testing (SRT and WRS), and pure-tone threshold testing (air and bone))• Hearing aid fitting is completed, and REM is completed.• Speech in noise task is completed.• Live preference ratings are completed
Visit 2 Approximately 2 Hours	
• Streamed preference ratings are completed.• At the end of data collection, participant will be debriefed and compensated for their time

3 Statistical design and analysis

3.1 Determination of Sample Size

We will recruit 25 participants for all tasks. To obtain a power of 90% with 10% of risk of running into beta error (i.e., miss) and with 5% risk of running into alpha error (i.e. false alarm), the power analysis estimated the total sample size to be 25, leading to an actual power of 90%.

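### Section 3.1 states a 5% false-alarm risk, but the primary rule in 3.3.2 names the top of three tallies with no test and no control over the three pairs, so the plan does not deliver that 5%

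*Combined protocol and SAP*

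**What the plan says.** Section 3.1 gives one set of error rates for the whole study: "To obtain a power of 90% with 10% of risk of running into beta error", "with 5% risk of running into alpha error (i.e. false alarm"). It then reports that "the power analysis estimated the total sample size to be 25, leading to an actual power of 90" per cent. It does not name the test, the effect size, whether the test is one- or two-sided, or the endpoint. The sample applies to everything: "We will recruit 25 participants for all tasks".

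Section 2.1.1 sets the number of curves: "There are three gain curves that will be tested for the streaming task (Variations #1, #2, and #3"). Section 3.3.2 makes the streaming task primary. Samples are heard two at a time, the preferred one scores 1, and neither scores if the listener notices no difference. "There will be 3 different samples", and "the maximum value would be 2 (implying that the sample was preferred in all trials in which it was involved"), which fits one judgement per pair. The decision rule is: "Subjective ratings will be tallied to see which frequency response curve was preferred the most". No hypothesis test, p-value, threshold or multiplicity rule follows.

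Section 1.2 frames the primary objective as changed curves against the current streaming program. The documents do not say which of the three variations, if any, is that program. Section 1.1 calls the study exploratory and says it is meant to show whether new curves are worth putting into products.

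**The concern.** A 5% false-alarm risk means that a preference is declared no more than one time in twenty when none exists. A rule that reports whichever of three totals is largest cannot have that property, because some total is nearly always largest.

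Naming a pairwise test would not be enough. Three curves give three pairs, and a separate 5% test on each spends the 5% more than once. The number of curves needs its own rule, in addition to the choice of test. At stake is whether a chance ordering of three curves is reported as a preference, with an error rate beside it that suggests it has been guarded against.

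**Working it through.** **Inputs from the documents.** N = 25, alpha 5%, power 90% (3.1); three curves (2.1.1); pairwise choices, score 0 to 2, no-difference answers allowed (3.3.2).

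**Assumptions.** Each listener judges each pair once, tallies are summed over listeners, and the null is no true preference. Where a pairwise test is needed, it is the exact two-sided sign test with no-difference answers dropped. The no-difference rate is not given; 0% and 20% are shown. Under the null, listeners either choose independently on each pair or hold a consistent but random ranking.

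**1. The plan's own figure.** N = 25 at 90% power cannot be reproduced, because the test and effect size are missing. Solving backwards, several inputs fit:
- paired t-test, two-sided, standardized difference about 0.68 (one-sided, about 0.60);
- sign test, true preference about 80%;
- repeated-measures ANOVA, three conditions, f = 0.30, correlation 0.5: noncentrality = f² × N × 3 / (1 − 0.5) = 0.09 × 25 × 3 / 0.5 = 13.5 on 2 and 48 degrees of freedom, power 0.900.

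So 3.1 does not reveal which procedure its 5% describes.

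**2. The rule as written.** Simulating 25 listeners under the null (100,000 trials per setting), one curve alone has the highest tally in 91% to 92% of trials without no-difference answers, and in 90% to 91% when 20% of answers are no difference.

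**3. If each pair were tested at two-sided 5%.** With 25 choices the sign test rejects at 18 or more for either curve. Its size is 2 × P(X ≥ 18 | 25, 0.5) = 2 × 0.0216 = 0.0433.

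| Chance of at least one false difference | Three pairs | Two contrasts with one reference |
|---|---|---|
| Formula, independent pairs | 1 − (1 − 0.0433)³ = 12.4% | 1 − (1 − 0.0433)² = 8.5% |
| Simulated, consistent random rankings | 11.7% | 8.3% |
| Simulated, 20% no-difference answers | 8.3% to 8.6% | 5.7% to 5.8% |

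**4. Direction.** These figures count differences either way. If one curve is the current program, the chance that a new curve falsely beats it is 1 − (1 − 0.0216)² = 4.3%.

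**5. With an overall test first.** When the pairs are tested only after a significant Friedman test on the per-participant tallies, the chance of any false pairwise difference under the null is about 3% to 5% in all these settings.

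**6. Power for an 80:20 pair, A over C.** Ungated, it is P(X ≥ 18 | 25, 0.8) = 89%. With the gate:

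| Third curve B | Gated power, A versus C |
|---|---|
| A preferred 80:20 to both B and C, which are even | about 89% |
| B between them, 60:40 on each side | about 82% |
| Only A versus C differs (intransitive) | about 61% |

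**The case against.** The strongest objection is that no false-alarm rate can be charged to a plan that performs no test. A reader might infer that the true risk is about 12% rather than 5%. The documents do not support that: 12% belongs to three unadjusted two-sided sign tests that they never mention. Nor do they exclude the possibility that the 5% already covers all three curves, since a three-condition overall test fits N = 25 exactly under the assumed f and correlation. Both points stand, so the pairwise figures are only conditional. Neither point supplies the missing rule: 3.3.2 mentions no overall test, and if one was intended, writing it down is the correction.

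A reader might also infer that a new curve would be adopted by chance at more than twice the stated rate. That does not follow. The 12.4% counts new curves losing and new curves differing from each other. A false win over a current program comes to 4.3% under the same test.

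Lastly, the study is exploratory, and exploratory work need not control family-wise error. That is fair, and it makes dropping the claim a legitimate choice. It does not justify quoting 5% and 90% beside a named primary endpoint whose rule carries neither.

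**Conclusion.** The concern holds as a mismatch between 3.1 and 3.3.2: the stated 5% is not a property of the written primary rule. Taken literally, that rule gives a sole top curve in about 90% of trials with no true preference, assuming one judgement per pair and tallies summed over 25 listeners. If each pair were tested at two-sided 5%, the chance of at least one false difference would be about 8% to 12% over three pairs. It would be about 6% to 9% over two contrasts, if one curve is the current program. These ranges rest on the assumed sign test and on no-difference rates of 0% to 20%. No single replacement for the 5% can be read from the documents.

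**What to change.** In 3.3.2, replace the highest-tally rule with two steps:

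1. Run a Friedman test on the three per-participant tallies (participant as block, tie-corrected) at the 5% level. The test has no direction, so this corresponds to a two-sided 5%. If it is not significant, report that no streaming curve is shown to be preferred.
2. Only if it is significant, test the pairs with exact sign tests at two-sided 5% each.

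In 3.1, state that the 5% refers to this procedure for the streaming task, and that the live-preference and speech results are secondary and outside it.

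Add one clause on the assumption behind the control. With three curves and consistent (transitive) preferences, once the curves are not all equal at most one pair can still be even, so no further adjustment is needed. If preferences are intransitive, two pairs can be even while the third is not; the gate may then pass almost always, and the family error approaches the two-pair 8.5%.

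The cost is a few sentences and no extra participants, visits or data. Power for an 80:20 pair is almost unchanged when one curve stands apart from the other two, but falls by about 7 points (89% to 82%) when the third lies between at 60:40, and further if preferences are intransitive.

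If the sponsor prefers to keep the tally as an exploratory description, 3.1 should drop the 5% false-alarm claim for it. It should not insert an assumption-dependent figure in its place.

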3.2 Statistical criteria of termination of trial

N/A

3.3 Planned Analyses

3.3.1 Datasets to be analyzed, analysis population

Datasets to be analyzed:

- Demographic information (e.g., hearing profiles, listening experience, hearing aid experience, age, etc.) will be analyzed
- Subjective ratings provided by participants when listening to acoustic or streaming signals
- Objective scores collected from speech in noise test

3.3.2 Primary Endpoint Analysis

The primary analysis will be the subjective ratings participants provide for the streaming task. Subjective ratings will be tallied to see which frequency response curve was preferred the most. Participants will be presented with two samples at a time and will choose which sample they prefer. For example, if Sample A was preferred over Sample B, then Sample A gets a score of 1. If Sample B was preferred over Sample A, then Sample B gets a score of 1. In some trials, if the participant does not notice a difference between the two samples, then neither sample will get a score. At the end of the task, scores will be tallied to determine which sample was preferred the most overall. There will be 3 different samples. The minimum value for the tallied score would be 0 (the sample was not preferred at all) and the maximum value would be 2 (implying that the sample was preferred in all trials in which it was involved). Higher scores mean that the sample was preferred more and lower scores mean the sample was not preferred as much when compared to the other samples.

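### Streaming task: a no-difference answer scores the same as a loss, so unequal tie rates between the three pairs can put the wrong curve first

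*Combined protocol and SAP*

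**What the plan says.** Section 3.3.2 (Primary Endpoint Analysis) describes a paired-comparison task: "There will be 3 different samples", shown two at a time. On scoring, "if Sample A was preferred over Sample B, then Sample A gets a score of 1", and the sample not chosen gets nothing. For a tie, "if the participant does not notice a difference between the two samples, then neither sample will get a score". Each curve is in two pairs, so its score runs from 0 to 2 per participant.

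The section then says that "scores will be tallied to determine which sample was preferred the most overall", and that "lower scores mean the sample was not preferred as much when compared to the other samples". No other section gives a different tie rule, a separate count of ties, a denominator of decided comparisons, or a model for paired comparisons.

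**The concern.** A win scores 1; a loss and a tie both score 0. A low total may mean that listeners rejected the curve, or that they could not tell it from another. The plan reads it only as weaker preference.

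With three curves this can change the ranking. A pair hands out only as many points as it has decided answers. If two curves sound alike and the third is distinct, the similar pair hands out few points, and both its members fall behind the third whatever listeners think of it. The tally is the whole of the stated primary analysis, in a study meant to inform whether new gain curves should be implemented (section 1.1). A curve that lost both its head-to-head comparisons could be named the most preferred, or a curve that won both could be pushed down.

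**Working it through.** **Inputs from the documents.** Three curves, hence three pairs, with each curve in two; win 1, loss 0, tie 0 (section 3.3.2); 25 participants (section 3.1). Enumerating the 3 × 3 × 3 = 27 possible answer patterns of one participant reproduces the stated 0 to 2 range. In none of the 27 does a curve that loses both its pairs rank first. The problem therefore arises only when scores are combined over participants.

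**Assumptions.** Scores are summed over participants (averaging gives the same ranking). Tie rates and preference strengths are not in the documents and are varied below.

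**Why ties matter.** Compare the planned score with one giving 0.5 to each sample for a tie:

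planned score − half-point score = −(ties in the curve's two pairs)/2

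The curve with the fewest ties gains on the others, irrespective of preference.

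**Count example, a distinct curve favoured.** All 25 participants hear #1 and #2 as equal, and each beats #3 by 14 to 11.
- Planned: #1 = 14, #2 = 14, #3 = 11 + 11 = 22. Curve #3 is first, having lost both pairs.
- Half points: #1 = #2 = 14 + 25/2 = 26.5, #3 = 22.

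**Count example, a winner pushed down.** #1 beats #2 by 13 to 12; #3 beats each of them 9 to 6 with 10 ties.
- Planned: #1 = 13 + 6 = 19, #2 = 12 + 6 = 18, #3 = 9 + 9 = 18.
- Half points: #1 = 19 + 5 = 24, #2 = 18 + 5 = 23, #3 = 18 + 10 = 28.

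**Threshold in expectation.** Let t be the tie rate in #1–#2, s the tie rate in each pair with #3, and p the share preferring #1 (or #2) to #3 among decided answers, with #1–#2 evenly split. Per participant, #1 expects (1 − t)/2 + p(1 − s) and #3 expects 2(1 − p)(1 − s). So #1 out-scores #3 only if

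p > 2/3 − (1 − t)/(6(1 − s))

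- t = 0.2, s = 0: 0.667 − 0.133 = 0.533
- t = 0.6, s = 0: 0.667 − 0.067 = 0.600
- t = 0.6, s = 0.3: 0.667 − 0.095 = 0.571
- t = s: 0.500, the fair value

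**Simulation.** 400,000 runs per scenario, n = 25, each pair judged once per participant, pairs independent, p = 56%, and first meaning strictly highest.

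| Ties #1–#2 | Ties in #3's pairs | #3 first, planned | #3 first, half points | Planned: #3 first after losing both pairs |
|---|---|---|---|---|
| 10% | 0% | 14% | 10% | 0.06% |
| 20% | 0% | 20% | 10% | 0.6% |
| 60% | 0% | 54% | 11% | 16% |
| 20% | 10% | 15% | 11% | 0.07% |
| 40% | 20% | 24% | 12% | 0.7% |
| 60% | 30% | 36% | 13% | 2.7% |
| 30% | 30% | 12% | 12% | 0.03% |
| 60% | 60% | 15% | 16% | 0.06% |

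Mirror case: #3 is preferred to each rival by 56%, with 20% ties in its own pairs and none in #1–#2. It comes first in 37% of studies under the planned tally and 58% under half points.

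Clearer preference (p = 70%), #3 first, planned against half points: 0.2% v 0.04% at ties of 20% and 0%; 0.7% v 0.1% at 40% and 20%; 2.3% v 0.3% at 60% and 30%; 3% v 0.05% at 60% and 0%.

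Half points never put first a curve that lost both pairs. Each of the three pairs hands out 25 points, 75 in all, so the average curve has 25. A curve losing both pairs has less than 12.5 from each, hence under 25, and some other curve must be above it.

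**The case against.** The strongest reply is that the harm needs materially unequal tie rates, and nothing in the documents shows that they will occur: the text says only that ties happen in some trials and does not describe how alike the three variations are. This stands, and it is why the size can only be given as a range. It does not make the rule safe, because equal tie rates across three different pairs become an unstated condition for a fair ranking.

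It is also true that the worst outcome, a curve ranked first after losing both pairs, stays below 1% when ties between #1 and #2 are 40% or less in the scenarios above, and that a 56% preference (14 to 11 in 25) is close to indifference. At 70% the planned tally rarely fails.

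A third argument is that the plan openly counts wins, which is a legitimate summary for an exploratory study. That would be enough if the tally were read only as a count of wins, but section 3.3.2 also reads low scores as weaker preference relative to the other samples.

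Fourth, the primary objective in section 1.2 is a comparison with the current streaming program, and within a single pair the tie rule is symmetric and cannot reverse the direction. This is correct, but section 3.3.2 plans no results by pair; it plans the three-way total.

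Finally, half points have an ambiguity of their own: a curve that is always tied scores 1, the same as one win and one loss. This is a good reason to report the counts for each pair alongside the score.

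**Conclusion.** The concern holds and should be fixed. As written, the tie rule can misrank the three streaming curves when tie rates differ between pairs. Under near-even preferences (56%) and moderate tie gaps, it raises the chance that a less preferred but more distinct curve comes first from about 10–12% to 14–24%. With 60% ties in the similar pair the figure is 36–54%, against 11–13% under half points. It can also cost a truly preferred curve first place (37% against 58% in the mirror case). With equal tie rates there is no material distortion, and at 70% preference the planned tally put the less preferred curve first in no more than about 3% of studies.

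These figures rest on assumed tie rates, independent pairs, and scores pooled over participants, which is a reading of the plan; the 0 to 2 range it states is per participant. The scoring rule itself and the direction of the bias do not depend on those rates.

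**What to change.** In section 3.3.2, for the streaming task, give each sample 0.5 for a no-difference answer. Every comparison then distributes one point and the 0 to 2 range is kept. Alternatively, fit a paired-comparison model that allows ties (Bradley-Terry with the Davidson extension).

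In either case, report wins, ties and losses for each of the three pairs, and state that scores are pooled over participants if that is intended. The pair counts let a reader separate a curve that was heard as equal from one on which opinion was divided.

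The two-program live task in section 3.3.3 needs no change for ranking, because a tie there affects both programs equally.

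The cost is one or two sentences in the SAP and a rescoring of answers already given. No new data are needed.
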